#### 1. OBJECTIVES

## 1.1 Study Design

This is an open-label phase II study of ipilimumab with or without nivolumab for patients with relapsed or refractory (R/R) classic Hodgkin lymphoma (cHL).

Patients who have previously failed a PD-1 mAb will receive 4 cycles of ipilimumab monotherapy and then undergo a restaging PET scan. Patients achieving an objective response will continue ipilimumab maintenance therapy. Patients with SD or progressive disease (PD) (if clinically stable) will receive 4 cycles of combination therapy with ipilimumab and nivolumab followed by ipilimumab maintenance therapy. Patients who have progressive disease after fewer than 4 cycles of ipilimumab are also eligible to proceed to combination therapy with nivolumab and ipilimumab, if they are clinically stable. The primary endpoint will be objective response rate (ORR) to 4 cycles of ipilimumab monotherapy.

## 1.2 Primary Objectives

• To estimate the ORR of ipilimumab monotherapy in patients with R/R cHL who failed a PD-1 mAb

## 1.3 Secondary Objectives

- Best ORR, PRR, CRR assessed by PET/CT (using Lugano criteria and LYRIC criteria) after ipilimumab monotherapy
- Best ORR, PRR, CRR assessed by PET/CT (using Lugano criteria and LYRIC criteria) after ipilimumab and nivolumab combination therapy
- To evaluate the following outcomes among patients receiving ipilimumab maintenance:
  - o DOR and PFS (Lugano criteria and LYRIC criteria)
  - o OS
  - Above endpoints, stratified by best response to PD-1 mAb (non-responder versus responder)
- To evaluate the following outcomes among patients receiving re-induction with ipilimumab/nivolumab combination therapy:
  - o DOR and PFS (Lugano criteria and LYRIC criteria)
  - $\circ$  OS
  - Above endpoints, stratified by best response to PD-1 mAb (non-responder versus responder)
- To evaluate the safety of study treatment (within the entire study popultion, among patients receiving ipilimumab maintenance, and among patients receiving ipilimumab/nivolumab combination treatment) as measured by:
  - o Rate of grade 3 or higher toxicity regardless of attribution
  - o Rate of grade 3 or higher toxicity at least possibly related to study treatment
  - o Rate of grade 2 or higher toxicity at least probably related to study treatment

Protocol version date: v8/06 September 2023

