# Secondary Endpoints

- Best ORR, PRR, CRR assessed by PET/CT (using Lugano criteria and LYRIC criteria) after ipilimumab monotherapy
- Best ORR, PRR, CRR assessed by PET/CT (using Lugano criteria and LYRIC criteria) after ipilimumab and nivolumab combination therapy
- DOR (using Lugano criteria and LYRIC criteria) for patients receiving ipilimumab maintenance
- DOR (using Lugano criteria and LYRIC criteria) for patients receiving ipilimumab and nivolumab combination therapy
- PFS and OS (Lugano criteria and LYRIC criteria)
- Safety
- Above endpoints, stratified by best response to PD-1 mAb (non-responder versus responder)

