# 13.4 Analysis of Secondary Endpoints

Secondary endpoints include, response assessments including ORR (defined as partial response and complete response), the duration of response (DOR) among patients who have achieved a PR or CR (defined as the time from first response to progression or last follow-up), progression free survival (PFS) (defined as the time from treatment start to progression, death or last follow-up, whichever comes first), and overall survival (OS) (defined as time from treatment start to death or last follow-up). The safety of study will be assessed as measured by: the rate of grade 3 or higher toxicity regardless of attribution, the rate of grade 3 or higher toxicity at least possibly related to study treatment, and the rate of grade 2 or higher toxicity at least probably related to study treatment.

For patients who respond to treatment (complete or partial response), duration of response will be calculated from the date of response to the date of progression of disease. Patients still responding at date of last follow-up will be censored. PFS will be calculated as the time from start of treatment to the date of progression, death or last follow-up. OS will be calculated as the time from the start of treatment to the date of death or last follow-up. OS, PFS and DOR will be calculated using Kaplan-Meier methodology. 95% confidence intervals will be calculated for all secondary endpoints.

Correlative studies analyzing tissue samples using MIF and/or MIBI and circulating tumor DNA using next-generation sequencing based platforms are exploratory in nature. This testing is not powered to detect associations, but rather is designed to generate hypothesis for future studies. Completion of correlative studies will depend upon sample collection and budget considerations.

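### Section 1.3 defines PFS and OS only among patients who reach maintenance or re-induction, while sections 13.1 and 13.4 name no population and start the clock at treatment start

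*Combined protocol and SAP*

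**What the plan says.** Section 1.3 introduces DOR, PFS and OS twice, each time for a subset: "To evaluate the following outcomes among patients receiving ipilimumab maintenance" and "To evaluate the following outcomes among patients receiving re-induction with ipilimumab/nivolumab combination therapy". It has no PFS or OS objective for the whole cohort. The safety objective in the same section does name the whole cohort as well as the subsets: "within the entire study popultion, among patients receiving ipilimumab maintenance".

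Section 13.1 is worded differently. Its DOR endpoints name a subset, for example "DOR (using Lugano criteria and LYRIC criteria) for patients receiving ipilimumab maintenance". The line that follows them, "PFS and OS (Lugano criteria and LYRIC criteria", names none.

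Section 13.4 gives the time origins, again without a population: "PFS will be calculated as the time from start of treatment to the date of progression, death or last follow-up" and "OS will be calculated as the time from the start of treatment to the date of death or last follow-up". Section 11.1.2 instead counts both from randomization or registration. Section 13.5 defines a toxicity set and refers to evaluable patients for the primary endpoint, but gives no analysis set for PFS or OS.

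On patient flow, section 1.1 says: "Patients with SD or progressive disease (PD) (if clinically stable) will receive 4 cycles of combination therapy with ipilimumab and nivolumab". It also lets clinically stable patients who progress before completing four cycles move to the combination. Section 5 lists the other exits from therapy: toxicity, withdrawal, progression, physician decision and death.

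**The concern.** Membership of either group in section 1.3 is settled after treatment has begun, by response, clinical stability, tolerance and survival. The section 13.4 clock is already running by then. A curve drawn from treatment start in such a group credits its members with time they had to live through in order to be counted.

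Patients who leave induction without reaching either group appear in no PFS or OS estimate that section 1.3 calls for. They include the earliest deaths and the unstable progressors. If section 1.3 is followed as written, no PFS or OS figure describes a patient starting the response-adapted approach set out in section 2.4. That section also compares PFS across trials, and a subset PFS from this study would invite the same comparison on unequal terms.

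If sections 13.1 and 13.4 are followed instead, the problem largely disappears. The plan does not say which governs, so in an open-label trial the choice could be made after the data are seen.

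**Working it through.** **The plan's own figure.** The documents state no PFS or OS figure. The one design calculation (section 13.3: reject at 4 or more responses of 13, ORR 10% versus 40%) reproduces by exact binomial: P(X ≥ 4 | 13, 0.10) = 0.0342 and P(X ≥ 4 | 13, 0.40) = 0.8314, against the stated 0.034 and 0.83. Nothing below affects it.

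**Who falls where under section 1.3.**
- Objective response after induction: maintenance group.
- SD or PD, clinically stable, including PD before four cycles: re-induction group. Those who later receive maintenance also fit the maintenance wording, so the groups can overlap.
- Death, clinical instability, withdrawal or toxicity stop during the 12-week induction: neither group.

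**What a treatment-start clock does to each curve.**
- *OS, both groups:* patients had to be alive at entry, so the time up to entry is event-free by construction.
- *PFS, patients entering maintenance as responders:* they had to be progression-free at the restaging scan, so the same holds.
- *PFS, re-induction:* patients with PD on induction have a PFS event at or before entry, while patients with SD do not. The curve mixes events that precede re-induction with guaranteed event-free time, and so does not describe PFS on re-induction.

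**Size of the omission (illustration).** Inputs: n = 13 (section 13.2); k patients in neither group, assumed; a group rate of 70% at a fixed time, assumed.

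If all k are early events, the rate in all 13 is 0.70 × (13 − k)/13. If all k are event-free at that time, it is [0.70 × (13 − k) + k]/13.

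| k | all k early events | all k event-free |
|---|---|---|
| 0 | 70% | 70% |
| 1 | 0.70 × 12/13 = 64.6% | 9.4/13 = 72.3% |
| 2 | 0.70 × 11/13 = 59.2% | 9.7/13 = 74.6% |
| 3 | 0.70 × 10/13 = 53.8% | 10/13 = 76.9% |

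The group rate overstates by 5.4, 10.8 or 16.2 points in the first column for k = 1, 2 or 3. In the second column it understates.

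**How likely k ≥ 1 is.** With an assumed probability q per patient of entering neither group, P(at least one of 13) = 1 − (1 − q)^13. This is 48.7% at q = 5%, 74.6% at 10% and 94.5% at 20%.

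**Guarantee time (upper bound).** Assume exponential survival with median m, and that every event before L = 84/30.4375 = 2.76 months is left out. With the clock kept at treatment start, S(t | T > L) = exp[−(ln 2/m)(t − L)], so the apparent median is m + L. Assumed medians of 6, 12 and 24 months read as 8.8, 14.8 and 26.8. It is an upper bound because some early progressors enter re-induction before week 12.

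**The case against.** The strongest reply is that section 13 already implies an all-treated analysis. DOR is restricted to subsets there and PFS and OS are not, the origin is treatment start (or registration in section 11.1.2), and sections 5.7 and 10.3 plan survival follow-up for participants generally. This is a fair reading, and it means inflated reporting is a risk rather than a settled outcome. It does not remove the conflict with section 1.3, which names its populations explicitly and includes the whole cohort for safety but not for PFS or OS.

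The stakes are also limited. The primary endpoint is ORR to induction, PFS and OS carry no test or threshold, and section 13.3 makes the re-induction analysis descriptive. Subset objectives are legitimate in themselves. All of this stands, and it keeps the point at the level of the secondary endpoints.

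A reader might infer three stronger things that the documents do not support:
- *That everyone who fails induction is lost.* Sections 1.1, 5 and 5.1 send clinically stable patients with SD or PD to re-induction.
- *That leaving patients out always flatters the treatment.* A patient who stops for toxicity may do well, and PD before entry pulls re-induction PFS down.
- *That the loss can be estimated by adding the rates in section 2.4 (10-15% rapid progression, 8% discontinuation for adverse events).* The first comes from PD-1 blockade and would include stable progressors who are kept here. The second comes from a combination regimen with nivolumab continuing for up to 2 years. Neither is a loss rate for 12 weeks of ipilimumab alone.

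**Conclusion.** The point holds in this form: section 1.3 conditions PFS and OS on events after treatment start, sections 13.1 and 13.4 do not, and the origin differs again in section 11.1.2. Following section 1.3 with the section 13.4 clock gives guarantee-time bias in maintenance-group PFS and in the OS of both groups, and a re-induction PFS that cannot be interpreted.

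The size cannot be fixed from the documents. It runs from nothing (no patient left out) to roughly 5 to 16 points on a 70% rate for one to three patients left out, if all of them are early events. It shrinks, vanishes or reverses if those patients do well. A reader might conclude that the published survival will look too good; that follows only if section 1.3 is taken to override section 13 and the omitted patients fare badly. With 13 patients, though, a single omission can move a rate by about 5 points, so the population should be settled before analysis.

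**What to change.** Reconcile sections 1.3, 11.1.2, 13.1 and 13.4:
- Make PFS (by Lugano and by LYRIC) and OS in all patients who receive at least one dose of ipilimumab, timed from first dose, the main secondary PFS and OS analyses.
- Keep the maintenance and re-induction analyses as descriptive, each timed from the start of that phase (landmark). State whether re-induced patients who go on to maintenance count in the maintenance group.
- Report how many patients entered neither group, with the reason and outcome for each.

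The cost is a few lines of protocol text and one extra Kaplan-Meier analysis, on follow-up already planned. The headline PFS and OS may be less favourable. Sample size, alpha and power do not change.

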## 1.4 Exploratory Objectives

- To determine if features of the cHL TME are associated with response or resistance to study treatment
- To determine if early reduction in ctDNA is associated with improved PFS.
- To characterize the genetic bases of immune evasion and correlate these alterations with responses to therapy

#### 2. BACKGROUND

## 2.1 Classic Hodgkin Lymphoma

Classic Hodgkin lymphoma (cHL) is diagnosed in approximately 8,500 people in the United States each year and is one of the most common cancers among young adults(1). The majority of patients are cured with first-line therapy, but approximately 10-15% of patients with early stage cHL and 15-30% of patients with advanced stage cHL will have primary refractory lymphoma or experience recurrence. Many of these patients may be cured with salvage chemotherapy and consolidative autologous stem cell transplantation (ASCT), but a significant cohort of patients are ineligible for these curative treatments due to chemoresistance, age, or comorbidities, or will relapse following ASCT.

Historically, patients who are ineligible for or relapse following ASCT have experienced poor outcomes with a median OS of approximately 2 years(2). With the development of new, highly active agents, however, the prognosis of chemotherapy-resistant disease has improved dramatically. Initial trials of brentuximab vedotin (BV) and PD-1 mAbs demonstrated high ORRs in patients with chemotherapy-resistant disease, however, CRRs are low (30-35% for BV and 15-25% for PD-1 mAbs) and a large majority of patients eventually relapse following these treatments(3–5). Currently, there are no therapies approved for progression after BV and PD-1 blockade. Depth of response appears to be a predictor of response duration for PD-1 mAbs. In the phase II trial of nivolumab, patients achieving a CR had more prolonged PFS compared to patients achieving a PR or stable disease(3). Novel treatment strategies are needed for patients who achieve an incomplete response or who experience progression on PD-1 blockade.

### 2.2 Ipilimumab

#### 2.2.1 Mechanism of Action

Ipilimumab has specificity and high affinity for human CTLA-4. Ipilimumab completely blocked binding of B7.1 and B7.2 to human CTLA-4 at concentrations higher than 6 ug/mL and 1 ug/mL, respectively. Data suggests that treatment with ipilimumab has a low ability to elicit effector functions able to deplete activated T cells in vivo.

### 2.2.2 Non-clinical Pharmacology

The half-life of ipilimumab in cynomolgus monkeys was long ( $203 \pm 62.8$  to  $339 \pm 112$  hours). Consistent with the long half-life, the total plasma clearance after a single dose of ipilimumab was low ( $0.196 \pm 0.037$  mL/h/kg). The steady state volume of distribution,  $44.1 \pm 6.05$  mL/kg, was similar to the reported plasma volume of monkeys, suggesting that ipilimumab remained in the vascular system.

In accordance with regulatory guidelines for biotechnology-derived pharmaceuticals, no tissue distribution studies with ipilimumab have been conducted in animals. However, the low volume of distribution in cynomolgus monkeys (0.046 to 0.060 L/kg) for each study drug indicates that there is little extravascular distribution of the drug. The expected in vivo degradation of mAbs is to small peptides and amino acids via biochemical pathways that are independent of cytochrome P450 enzymes.

## 2.2.3 Clinical Pharmacology

Ipilimumab has a terminal half-life of approximately 15.4 days. A population PK analysis of ipilimumab (n=785) demonstrated that the PK of ipilimumab is linear and exposures are dose proportional across the tested dose range of 0.3 to 10 mg/kg. Upon repeated dosing of ipilimumab, administered every three weeks, minimal systemic accumulation was observed by an accumulation index of 1.5-fold or less and ipilimumab steady-state concentrations were achieved by the third dose.

The effects of various covariates on the PK of ipilimumab were assessed in population PK analyses. The clearance of ipilimumab increased with increasing body weight supporting the recommended body weight (mg/kg) based dosing. The following factors had no clinically important effect on the clearance of ipilimumab: age (range: 23 to 88 years), sex, performance status, renal impairment, mild hepatic impairment, previous cancer therapy, and baseline lactate dehydrogenase (LDH) levels. The effect of race was not examined due to limited data available in non-Caucasian ethnic groups.

Renal Impairment: The effect of renal impairment on the clearance of ipilimumab was evaluated in patients with mild, moderate, and severe renal impairment compared to patients with normal renal function in population PK analyses. No clinically important differences in the clearance of ipilimumab were found between patients with renal impairment and patients with normal renal function

Hepatic Impairment: The effect of hepatic impairment on the clearance of ipilimumab was evaluated in patients with mild hepatic impairment (n=76) compared to patients with normal hepatic function (n=708) in the population PK analyses, and no clinically important differences in the clearance of ipilimumab were found. Ipilimumab has not been studied in patients with moderate or severe hepatic impairment.

## 2.2.4 Safety and clinical activity

The overall safety experience with ipilimumab, as a monotherapy or in combination with other

therapeutics, is based on experience in dozens of clinical trials and post-approval safety monitoring. For monotherapy, the safety profile is similar across tumor types. In Phase 3 controlled studies, the safety profile of ipilimumab monotherapy is acceptable in the context of the observed clinical efficacy, and manageable using established safety guidelines. Clinically relevant AEs typical of stimulation of the immune system were manageable by delaying or stopping ipilimumab treatment and timely immunosuppressive therapy or other supportive care.

Several small studies have tested ipilimumab as a single agent in patients with cHL (see section 2.3). More extensive information regarding safety and clinical activity is available for other cancer histologies, in particular, melanoma. The safety and efficacy of adjuvant ipilimumab therapy was tested in randomized phase III trial among patients with resected stage III cutaneous melanoma (NCT00636168). Patients were randomized to receive ipilimumab 10 mg/kg or placebo as an intravenous infusion every 3 weeks for 4 doses, followed by ipilimumab 10 mg/kg or placebo every 12 weeks from Week 24 to Week 156 (3 years) or until documented disease recurrence or unacceptable toxicity. Ipilimumab treatment was associated with an improvement both recurrence-free survival (HR 0.75, p<0.002) and overall survival (0.72, p<0.002). Among the patients treated with ipilimumab, the most frequent adverse events included pruritus (41%), diarrhea (39%), fatigue (38%), rash (38%), headache (31%), weight loss (31%), nausea (24%), ALT elevation (16%), abdominal pain (14%), pyrexia (14%), cough (14%), decreased appetite (14%), AST elevation (12%), hypophysitis (13%), and vomiting (12%). Grade 3+ adverse events occurring in more than 1% of patients included: diarrhea (10%), colitis (7%), hypophysitis (5%), ALT elevation (5%), AST elevation (4%), pruritus (2%), fatigue (2%), rash (1%), nausea (1%), and pyrexia (1%)(6). Rates of irAEs and treatment discontinuation are lower when ipilimumab is dose at 3 mg/kg (7).

#### 2.3 Nivolumab

#### 2.3.1 Mechanism of Action

Nivolumab is an IgG4 antibody which binds to PD-1 (Programmed cell death protein 1; CD279) with nanomolar affinity and shows a high degree of specificity for PD-1 – blocking binding of PD-1 to PD-L1 and PD-L2. Nivolumab binds to human PD-1 and not to other members of the CD28 family, such as ICOS, CTLA-4 or BTLA. Binding of the PD-1 ligands, PD-L1 and PD-L2, to the PD-1 receptor found on T cells, inhibits T cell proliferation and cytokine production. Upregulation of PD-1 ligands occurs in some tumors and signaling through this pathway can contribute to inhibition of active T-cell immune surveillance of tumors.

### 2.3.2 Non-clinical Pharmacology

Cynomolgus monkeys received single IV doses of nivolumab at 1 mg/kg (3 males and 3 females) and 10 mg/kg (3 males). Nivolumab was immunogenic in this study: 5 of 6 animals administered doses of 1 mg/kg and 2 of 3 animals administered doses of 10 mg/kg tested positive for antinivolumab antibodies (determined to be neutralizing antibodies) 27 days after dosing. Nivolumab concentrations declined in a multi-phasic manner from the maximum concentration, which was observed at 0.25 to 0.5 hours. Concentrations were measurable through a median time of 384 hours for males and females at 1 mg/kg and through 648 hours for males at 10 mg/kg. The

apparent elimination half-life estimates for males and females at 1 mg/kg were similar, at 124 and 139 hours, respectively. The T-HALF estimate at 10 mg/kg for males was 261 hours, but the data were variable (SD = 200 hours). Consistent with the long half-life, total serum clearance was low. Systemic exposure to nivolumab increased in an approximately dose proportional manner.

## 2.3.3 Clinical Pharmacology

Nivolumab pharmacokinetics (PK) were assessed using a population PK approach for single-agent nivolumab. The PK of nivolumab was studied in patients over a dose range of 0.1 mg/kg to 20 mg/kg or as a flat dose of 240-480mg administered as a single dose or as multiple doses of nivolumab as a 60-minute intravenous infusion every 2 or 4 weeks. The exposure to nivolumab increases dose proportionally over the dose range of 0.1 to 10 mg/kg administered every 2 weeks. The predicted exposure of nivolumab after a 30-minute infusion is comparable to that observed with a 60-minute infusion. Steady-state concentrations of nivolumab were reached by 12 weeks when administered at 3 mg/kg every 2 weeks, and systemic accumulation was 3.7-fold.

*Distribution:* The geometric mean volume of distribution at steady state and coefficient of variation is 6.8 L (27.3%).

Elimination: Nivolumab clearance decreases over time, with a mean maximal reduction from baseline values of 24.5% resulting in a geometric mean steady-state clearance of 8.2 mL/h in patients with metastatic tumors; the decrease in steady-state clearance is not considered clinically relevant. Nivolumab clearance does not decrease over time in patients with completely resected melanoma, as the geometric mean population clearance is 24% lower in this patient population compared with patients with metastatic melanoma at steady state. The geometric mean elimination half-life is 25 days.

Specific Populations: The following factors had no clinically important effect on the clearance of nivolumab: age (29 to 87 years), weight (35 to 160 kg), sex, race, baseline LDH, PD-L1 expression, solid tumor type, tumor size, renal impairment (eGFR greater than or equal to 15 mL/min/1.73 m²), and mild (total bilirubin [TB] less than or equal to the ULN and AST greater than ULN or TB greater than 1 to 1.5 times ULN and any AST) or moderate hepatic impairment (TB greater than 1.5 to 3 times ULN and any AST). Nivolumab has not been studied in patients with severe hepatic impairment (TB greater than 3 times ULN and any AST).

Drug Interaction Studies: When nivolumab 1 mg/kg was administered in combination with ipilimumab 3 mg/kg, the clearance of nivolumab was increased by 29% and the clearance of ipilimumab was unchanged compared to nivolumab administered alone. When nivolumab 3 mg/kg was administered in combination with ipilimumab 1 mg/kg, the clearance of nivolumab and ipilimumab were unchanged. When administered in combination, the clearance of nivolumab increased by 20% in the presence of anti-nivolumab antibodies.

